### **12.5.3 Overall survival (OS)**

OS is the time from date of tisagenlecleucel re-infusion to the date of death due to any reason. In case a patient is alive at the date of last contact on or before data cut-off, OS is censored at the date of last contact. No censoring will be done in case of SCT. Thus, patients should be followed-up for survival also in case of SCT.

### **12.5.4 Safety endpoints**

#### **12.5.4.1 Analysis set and grouping for the analyses**

For all safety analyses, the Safety Set will be used. The overall observation period will be divided into two mutually exclusive segments:

- pre re-infusion period: from day of patient's informed consent/assent to the day before re-infusion of tisagenlecleucel.
- post re-infusion period: starting at day of tisagenlecleucel re-infusion

#### **12.5.4.2 Adverse events (AEs)**

Reporting of adverse events will be based on MedDRA and CTCAE version 4.03. Treatment-emergent AEs are defined as AEs that started or worsened after tisagenlecleucel re-infusion. Summary tables for AEs will include only treatment emergent AEs. However, all safety data (including those from the pre re-infusion period) will be listed and those collected during the pre-infusion period are to be flagged. The incidence of treatment-emergent adverse events will be summarized by primary SOC, preferred term, severity (based on CTCAE grades), and relationship to tisagenlecleucel. Patients who experienced multiple AEs for a preferred term will be counted once for that preferred term, similarly for patients with multiple AEs per primary SOC. A patient with multiple CTC grades for an AE will be summarized under the maximum CTC grade recorded for the event. The frequency of Common Toxicity Criteria (CTC) grade 3 and 4 AEs will be summarized separately.

Deaths reportable as SAEs and non-fatal SAEs will be listed by patient and tabulated by type of AE.

**12.5.4.3 Adverse events of special interest (AESI) are defined by the important identified risk and important potential risk as presented in the effective Risk Management Plan (RMP). MedDRA search criteria to retrieve AEs indicative of these risks are updated on a regular basis at the tisagenlecleucel program level. The most recent version of the AESI search criteria form will be used for the reporting activity.**

**Laboratory abnormalities**

- For laboratory tests covered by the CTCAE, the study's biostatistics and reporting team will grade laboratory data accordingly. For laboratory tests covered by CTCAE, a Grade 0 will be assigned for all non-missing values not graded as 1 or higher. Grade 5 will not be used. For laboratory tests where grades are not defined by CTCAE, results will be graded by the low/normal/high classifications based on laboratory normal ranges. The following summaries will also be generated separately for hematology and biochemistry: shift tables using CTCAE grades to compare baseline to the worst post-infusion value
- for laboratory tests where CTCAE grades are not defined, shift tables using the low/normal/high/ (low and high)

**12.5.4.4 B-cell and T-cell level**

The levels of B and T cells (peripheral blood prior to and following tisagenlecleucel infusion) will be described. Baseline and absolute and relative change (percent change) from baseline will be calculated and summarized using sample size, mean, standard deviation, median, minimum and maximum. Baseline and change from baseline to minimum cell number may also be summarized by response status and potentially graphed using strip plots. Patient level and averaged cell counts and percent change from baseline may be displayed using longitudinal plots.

It is anticipated that all patients who achieve complete remission will exhibit B-cell aplasia. Timing of B-cell recovery will be summarized. CD8 and CD4 positive T cells will be listed and summarized by time point. Data may also be summarized by response status and potentially graphed using strip plots. Patient level and average longitudinal plots of the cell counts and percent changes from baseline may be generated. For abnormal T cell or B cell results, associated safety events such as infections and use of associated therapies (i.e. antibiotics, immunoglobulin replacement) will be investigated using patient listings. CKAS set will be used for the analysis of [REDACTED] and biomarkers.

**12.5.5 Pharmacokinetics**

Plasma concentration data will be listed by treatment, subject, and visit/sampling time point. Descriptive summary statistics will be provided by treatment and visit/sampling time point, including the frequency (n, %) of concentrations below the LLOQ and reported as zero for the Pharmacokinetic Analysis Set.

Summary statistics will include mean (arithmetic and geometric), SD, CV (arithmetic and geometric), median, minimum and maximum. Concentrations below LLOQ will be treated as zero in summary statistics and for PK parameter calculations.

### **12.5.6 Biomarkers**

Not applicable

### **12.5.7 PK/PD relationships**

Not applicable

### **12.5.8 Patient reported outcomes**

Not applicable

## **12.7 Interim analyses**

No formal interim analysis will be performed for this study. As required, interim analyses may be performed every six months annually for publication purpose.

### **12.8 Sample size calculation**

This study is an exploratory study to determine the safety and efficacy of tisagenlecleucel re-infusion with an early loss of B-cell aplasia.

Sample size was based on an exact test for single proportion to test the null hypothesis  $H_0: p \leq 0.10$ . Where  $p$  is the proportion of patients who establish B cell aplasia during 12 months. If the true rate  $p \geq 0.25$ , then with an one sided alpha level of 2.5% and at least 80% power, a minimum of 49 evaluable patients will be required for the study. Considering drop-out rate of 10%, a total of approximately 54 patients will be enrolled into the study.

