### 3 Study design

A phase II, open label, multi-center trial to determine the efficacy and safety of tisagenlecleucel re-infusion in pediatric and AYA patients with acute lymphoblastic leukemia experiencing loss of B-cell aplasia. The patient population for this study will be comprised of 49 evaluable patients up to and including 25 years of age who have been previously infused with commercial tisagenlecleucel and have an additional dose of commercial tisagenlecleucel available and prescribed by a physician in the course of medical practice

Additionally these patients must have loss of B-cell aplasia defined as:

- Peripheral blood (PB) absolute B lymphocyte count  $\geq 50/\mu\text{L}$ , OR
- PB B lymphocyte  $\geq 10\%$  of the total lymphocytes

Efficacy in this setting will be defined as establishing B cell aplasia.

The efficacy of the following sub populations will also be evaluated:

[figure not shown]
- Patients with a loss of B-cell Aplasia within 9 months of first infusion AND are MRD (+) at time of enrollment
- Patients with a loss of B cell aplasia very early ( $<3$ months), early ( $\leq 3$  to  $<6$ months) and later ( $\geq 6$  months) following first infusion

The study will have the following sequential phases for all patients: Screening ([Section 8.1.1](#)), Treatment and Follow-up ([Section 8.1.5](#)). The total duration of the study is about 12 months. After tisagenlecleucel re-infusion, efficacy will be assessed at months 1, 3, 6, and 12. Safety will be assessed throughout the study.

The end of the study will be when all patients complete a month 12 visit unless discontinuing prior as outlined in [Section 9.1](#). The patient may voluntarily withdraw from the study for any reason, at any time. Patients who receive commercial tisagenlecleucel must be followed for up to 15 years post-infusion. Patients can be followed under the Center for International Blood and Marrow Transplant Research (CIBMTR) cellular therapy registry if consented for participation. For patients who do not provide consent for participation in the Center for International Blood

and Marrow Transplant Research (CIBMTR) registry, AEs will need to be reported as outlined in [Table 16-1](#) per the Safety Reporting guidelines of 15 years or until the patient enrolls in the registry.

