## 5 Population

The target population consists of pediatric and adolescent young adult patients up to and including 25 years of age with B-cell ALL who have been previously infused once with tisagenlecleucel and have a loss of B-cell aplasia. Approximately 54 subjects will be enrolled to allow 49 subjects treated.

The investigator or designee must ensure that only subjects who meet all the following inclusion and none of the exclusion criteria at screening and prior to infusion are offered treatment in the study.

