#### **12.1.3 Full Analysis Set**

The Full Analysis Set FAS comprises all patients whom have received reinfusion of tisagenlecleucel.

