**12.4.3 Handling of missing values/censoring/discontinuations**

Patients in the study who are of unknown clinical response will be treated as non-responders. Other missing data are simply noted as missing on appropriate tables/listings.

Patients who proceed to HSCT while in remission after tisagenlecleucel re-infusion will be censored at the time of HSCT.

The volume of missing data generated due to the COVID-19 pandemic may also be assessed and sensitivity analyses will be performed, if deemed appropriate.

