2.6.2 Statistical hypothesis, model, and method of analysis

The primary efficacy analysis was to be performed by testing the following hypothesis:

- $H_0: p \leq 0.10$ vs. $H_A: p > 0.10$

The estimated proportion \hat{p} of patients who restore B-cell aplasia within 12 months following re-infusion with tisagenlecleucel will be presented together with an exact 95% Clopper-Pearson confidence interval (CI).

The null hypothesis was to be rejected if the lower limit of the 95% CI was greater than 0.10, demonstrating improvement after re-infusion. The estimated number of patients who restore B-cell aplasia required to reject the null hypothesis (H_0) is 10 (See Appendix [Section 5.4](#)).

The primary analysis will not be conducted as planned due to not enough patients enrolled for a meaningful analysis, based on early termination of the study as described above and in [Section 4](#). Data for the primary objective will be listed only.

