2.12 Interim analysis

No formal interim analysis was planned for this study. Interim analyses could have been performed half-yearly following study start as required for publication purposes; however, no interim analyses were actually required due to early termination of the study.

3 Sample size calculation

This study is an exploratory study to determine the safety and efficacy of tisagenlecleucel re-infusion with an early loss of B-cell aplasia. The primary efficacy variable is the proportion of patients who restore B-cell aplasia (as defined in [Section 2.6](#)) within 12 months following re-infusion.

Sample size was based on an exact test for single proportion to test the null hypothesis $H_0: p \leq 0.10$, where p is the proportion of patients recovering B-cell aplasia during 12 months. If the true rate $p \geq 0.25$, then with a one sided alpha level of 2.5% and at least 80% power, a minimum of 49 evaluable patients will be required for the study. Considering a drop-out rate of 10%, a total of approximately 54 patients will be enrolled into the study.

4 Change to protocol specified analyses

The HESTER Trial has enrolled 5 patients over the course of one year. Given this rate of enrollment, the ability to enroll the planned number of patients within a reasonable time period is no longer feasible. Therefore, after careful consideration, it was decided to close the trial. Data is not adequate to perform statistical analysis. All study data will be listed.

The decision to close the study is not based on any issues related to safety.

Primary endpoint updated by removing text “presence of CTL019 cells by qPCR in the peripheral blood” from B-cell aplasia definition.

5 Appendix

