5.4 Statistical models

Not applicable.

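### Is the stated power of at least 80% undermined by the undefined word evaluable, and the rejection count of 10 by having no sample size attached?

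*Protocol*

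**What the plan says.** Protocol 12.8 sizes the trial with an exact single-proportion test of a 10% null rate against a true rate of 25%, one-sided 2.5%, and concludes: "at least 80% power, a minimum of 49 evaluable patients will be required for the study". SAP Section 3 repeats the calculation and adds the allowance for losses: "Considering a drop-out rate of 10%, a total of approximately 54 patients will be enrolled into the study".

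The 49 is described in two ways. Protocol Section 3 says the population "will be comprised of 49 evaluable patients up to and including 25 years of age", and the Protocol summary also speaks of evaluable patients. Protocol Section 5 says: "Approximately 54 subjects will be enrolled to allow 49 subjects treated".

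The primary test uses the Full Analysis Set (FAS), which under Protocol 12.1.3 "comprises all patients whom have received reinfusion of tisagenlecleucel". Protocol 12.4.3 adds: "Patients in the study who are of unknown clinical response will be treated as non-responders".

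Under Protocol 12.4.2 and SAP 2.6.2, the null hypothesis is rejected when the lower limit of the exact 95% Clopper-Pearson interval exceeds 0.10. Directly after that rule, SAP 2.6.2 states: "The estimated number of patients who restore B-cell aplasia required to reject the null hypothesis", and gives it as 10. It refers to the appendix "5.4 Statistical models" for support, and that appendix is marked not applicable.

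**The concern.** There are two reasons for doubt.

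- **The unit of the 49.** Protocol Section 5 uses the whole step from 54 to 49 before treatment. The primary analysis then takes everyone re-infused and scores unknowns as failures. Read together, this leaves no allowance for patients whose B-cell status is never established after re-infusion. Because 49 is the minimum that reaches 80%, a single such patient might take the trial below its stated power.
- **The count of 10.** A rejection count belongs to one sample size or a narrow range of them. If three or fewer of the 54 enrolled were lost before re-infusion, the FAS would be 51 to 54. There, 10 responders no longer satisfy the interval rule printed beside the count. A reader who applied 10 as a rule would test at more than 2.5%, and the appendix that should explain the figure is empty.

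At stake would be an overstated power and a possible clash between two decision rules. Both could be carried into the study report, because SAP Section 1 says its text may serve as a first draft of the report's methods and sample-size section.

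**Working it through.** **Inputs.** Null rate 0.10, true rate 0.25, one-sided alpha 0.025, 49 patients, 10% drop-out and 54 enrolled (Protocol 12.8, SAP 3); rejection when the Clopper-Pearson lower limit exceeds 0.10 (Protocol 12.4.2); unknown counted as non-response (Protocol 12.4.3); count of 10 (SAP 2.6.2).

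**Formulas.** With X binomial:

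- critical count c(n) = smallest x with P(X ≥ x | n, 0.10) ≤ 0.025. This gives the same count as requiring a Clopper-Pearson lower limit above 0.10, at every n from 36 to 65;
- power = P(X ≥ c(n) | n, 0.25).

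**1. The plan's own figure.**

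| n | c(n) | Exact size | Power |
|---|---|---|---|
| 48 | 10 | 0.0187 | 79.5% |
| 49 | 10 | 0.0215 | 81.7% |
| 50 | 10 | 0.0245 | 83.6% |

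No n below 49 reaches 80%, so the stated minimum is exact. The lower limit for 10/49 is 0.1024, so 10 is the correct count at the planned size. For the inflation, 49/0.9 = 54.4, against a stated figure of approximately 54.

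**2. Unknown status after re-infusion, FAS of 49, threshold 10.** Two readings of the 25% are possible.

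- *25% among assessable patients only.* With k unknowns scored as failures, power = P(X ≥ 10 | 49 − k, 0.25). This gives 81.7% for k = 0, 79.5% for k = 1, 77.2% for k = 2 and 74.7% for k = 3.
- *25% on the endpoint as analysed, with unknowns already failures.* Power = P(X ≥ 10 | 49, 0.25) = 81.7%, however many of the failures are unknowns.

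Protocol 12.8 defines p as the proportion of patients who establish aplasia over 12 months, with no restriction to those assessed. The first reading therefore rests on the word evaluable alone. One more re-infused patient also offsets one unknown: an FAS of 50 with k = 1 gives P(X ≥ 10 | 49, 0.25) = 81.7%.

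**3. How readily a patient becomes unknown.** The endpoint is restoration at some point within 12 months. Protocol Table 8-1 schedules flow cytometry and qPCR after re-infusion at Day 28, Month 3 and Month 12, and unscheduled visits are allowed. A patient who leaves after one qualifying sample is still a responder, so leaving before Month 12 is not the same as unknown status.

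**4. Range over which 10 holds.** c(n) = 10 for n = 44 to 50, 9 for 37 to 43 and 11 for 51 to 57. Above 50:

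| FAS | Lower limit at 10 responders | Size if 10 were used | Power at the correct count of 11 |
|---|---|---|---|
| 51 | 0.0982 | 2.79% | 76.2% |
| 52 | 0.0963 | 3.15% | 78.5% |
| 53 | 0.0944 | 3.55% | 80.7% |
| 54 | 0.0925 | 3.98% | 82.7% |

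At each of these sizes the lower limit for 10 responders is below 0.10, so the interval rule does not reject. The test keeps its level without any help from the count. The dip in power at 51 and 52 is the usual saw-tooth of an exact binomial test.

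**The case for a change.** The best case for a change is that every piece of it is true. Sizing on evaluable patients most naturally means patients whose outcome is known. Protocol Section 5 does place the losses before treatment, and no analysis set uses the word evaluable. On that reading the 80% claim depends on a condition that is never written down, and two unknowns cost 2.8 points against the target (80.0 − 77.2). The count of 10 is wrong for an FAS of 51 to 54, which is within reach of 54 enrolled, and its derivation cannot be found. Correcting this would cost only words, and the SAP text may pass into the study report.

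The facts stand; the need for a change does not. The shortfall appears on one of two admissible readings of the 25%, and the documents do not settle which was meant. Writing conditional powers such as 79.5% into the sample-size statement would present one reading as the plan. Nor is the allowance clearly spent before re-infusion: Protocol 12.8 and SAP 3 speak of drop-out without placing it in time. The SAP calls 10 an estimated number and sets it after the interval rule, so it illustrates the planned 49 and is no second criterion. The empty appendix fits an amendment that cut the SAP down to listings. As for the study report, that section records what was planned, and SAP Section 1 already foresees review and updating of the text before it is used there.

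**Conclusion.** The concern does not call for a change. The design calculation is right: 49 patients, threshold 10, size 2.15%, power 81.7%. The possible loss of power is 2.1 points for one unknown patient (81.7 − 79.5 from unrounded values, 81.66 − 79.52) and 4.5 points for two (81.66 − 77.19). It arises only if 25% is the rate among assessable patients and the unknown patients left no qualifying sample; otherwise it is nil. The count of 10 matches the planned 49, and the Clopper-Pearson rule gives the correct decision at any other FAS size, so an analyst following the plan would reach a sound conclusion.

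The remaining points are clerical: an undefined word, a count without its n and a dead cross-reference. They affect no result. SAP 2.6 and Section 4 record that the trial closed with 5 of 54 patients enrolled, that the primary test will not be run and that the data will only be listed.

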## **13 Ethical considerations and administrative procedures**

### **13.1 Regulatory and ethical compliance**

This clinical study was designed and shall be implemented, executed and reported in accordance with the ICH Harmonized Tripartite Guidelines for Good Clinical Practice, with applicable local regulations (including European Directive 2001/20/EC, US CFR 21), and with the ethical principles laid down in the Declaration of Helsinki.

### **13.2 Responsibilities of the investigator and IRB/IEC**

Before initiating a trial, the investigator/institution must obtain approval/favorable opinion from the Institutional Review Board/Independent Ethics Committee (IRB/IEC) for the trial protocol, written informed consent form, consent form updates, subject recruitment procedures (e.g., advertisements) and any other written information to be provided to subjects. Prior to study

start, the investigator is required to sign a protocol signature page confirming his/her agreement to conduct the study in accordance with these documents and all of the instructions and procedures found in this protocol and to give access to all relevant data and records to Novartis monitors, auditors, Novartis Quality Assurance representatives, designated agents of Novartis, IRBs/IECs, and regulatory authorities as required. If an inspection of the clinical site is requested by a regulatory authority, the investigator must inform Novartis immediately that this request has been made.

### **13.3 Publication of study protocol and results**

The protocol will be registered in a publicly accessible database such as clinicaltrials.gov and as required in EudraCT. In addition, after study completion (*defined as last patient last visit*) and finalization of the study report the results of this trial will be submitted for publication and posted in a publicly accessible database of clinical trial results, such as the Novartis clinical trial results website and all required Health Authority websites (e.g. Clinicaltrials.gov, EudraCT etc.).

This study only involves healthy volunteers and as such Novartis/sponsor will register the protocol as required to databases specified by local regulations (e.g. EudraCT during CTA filing for studies in EU/EEA). After study completion (*defined as last patient last visit*) and finalization of the study report, results of this trial may be submitted for publication (e.g. peer-reviewed journal) or registered to databases where required by local regulations.

For details on the Novartis publication policy including authorship criteria, please refer to the Novartis publication policy training materials that were provided to you at the trial investigator meetings.

### **13.4 Quality Control and Quality Assurance**

Novartis maintains a robust Quality Management System (QMS) that includes all activities involved in quality assurance and quality control, to ensure compliance with written Standard Operating Procedures as well as applicable global/local GCP regulations and ICH Guidelines.

Audits of investigator sites, vendors, and Novartis systems are performed by auditors, independent from those involved in conducting, monitoring or performing quality control of the clinical trial. The clinical audit process uses a knowledge/risk based approach.

Audits are conducted to assess GCP compliance with global and local regulatory requirements, protocols and internal SOPs, and are performed according to written Novartis processes

## **14 Protocol adherence**

This protocol defines the study objectives, the study procedures and the data to be collected on study participants. Additional assessments required to ensure safety of subjects should be administered as deemed necessary on a case by case basis. Under no circumstances including incidental collection is an investigator allowed to collect additional data or conduct any additional procedures for any purpose involving any investigational drugs under the protocol, other than the purpose of the study. If despite this interdiction prohibition, data, information, observation would be incidentally collected, the investigator shall immediately disclose it to

Novartis and not use it for any purpose other than the study, except for the appropriate monitoring on study participants.

Investigators ascertain they will apply due diligence to avoid protocol deviations. If an investigator feels a protocol deviation would improve the conduct of the study this must be considered a protocol amendment, and unless such an amendment is agreed upon by Novartis and approved by the IRB/IEC and health authorities, where required, it cannot be implemented.

